This experimental protocol will be carried out at the [name] Lab, Toronto Rehabilitation Institute to ensure any medical emergencies can be promptly cared for. Following the completion of the preliminary intake forms and participant debriefing, informed consent will be obtained. Each participant will be seated upright with their hands comfortably on their lap in a chair that has a high supportive back. They will be asked to relax their neck and shoulder muscles. A member of the research team will then apply the inclusion and exclusion criteria. The presence of a MTrP will be assessed by palpation of the upper trapezius muscle since this is the current method utilized in clinical practice. If there is a MTrP, then they will be asked to withdraw from the study since they do not satisfy the inclusion and exclusion criteria.

Participants will sit on a chair with one arm extended downward, and with the other arm on an armrest of the chair. The extended arm will be fixed by a wristcuff and a chain down to the floor, with a loadcell between the floor and the end of chain. The loadcell will measure the exerted force. The anatomical location for ultrasound probe and electrode placement will be identified for each participant. The ultrasound probe will be placed on 3 muscles: the trapezius, the supraspinatus, and the infraspinatus. Two ultrasonic pictures will be taken of each. Care will be taken to image the region of the muscle that was not mechanically impacted by the insertion of the needle or injection of the substance. The area will then be cleaned with alcohol and water. The Delsys Galelio surface sensor, and the intramuscular needle electrode will be placed directly on the trapezius' identified area. Participants will be asked to gently contract their trapezius muscle. They will be instructed to perform a gradually increasing contraction in isometric condition, in a controlled manner with a monitor showing the exerted force as well as the target force. They will hold this contraction at 30% of their maximal voluntary contraction, and then

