perform a gradually decreasing contraction to rest. This will be performed four times for each type of study intervention and before as well as after each intervention, namely topical control cream, topical capsaicin at 50ug and 100 ug, injection of the superior aspect of the superior fascia followed by intramuscular injection with these two concentrations of capsaicin. The placement of these latter will be verified by ultrasound guidance. The intramuscular needle will then be removed and participants will be bandaged and cared for appropriately by the expert physician performing the experiment. Following this, ultrasound pictures will be taken again from the same muscles mentioned previously. Participants will be re-examined to determine if there were any adverse effects from the experimental procedures. If any occurred, then these will be carefully managed by the medical members of the research team and recorded. Participants will be asked to remain at the lab for an additional 30 minutes to ensure they are well prior to leaving (Figure 2).

Central sensitization and measurement techniques

Inducing central sensitization

Central sensitization will be induced using capsaicin according to the established technique.[13,24,25] It induces increased pain severity at high doses relative to heat and elicits a dose dependent pain responses, allowing for more easily quantifiable measurements.[26] Capsaicin delivery induces both primary and secondary nociception suggesting that central mechanisms are involved in the nociceptive response, also termed as central sensitization.[13,14] Previous evidence has confirmed that capsaicin can sensitize nociceptive and mechanoheat receptors outside of the region of primary hyperalgesia, with speculation that it can also sensitize chemonociceptive receptors.[13] Therefore, capsaicin can effectively be used to induce central sensitization.

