The Sonosite Ultrasound machine located at the Toronto Rehabilitation Institute clinic will be used. The ultrasound probe will be placed onto the trapezius before and after the sensitization is induced and an ultrasonic image will be captured. Texture feature analysis will be performed using MATLAB and the Signal Processing Toolbox. Analyses will include first order parameters such as mean and standard deviation of the pixel level values, as well as second order parameters, which provide details on the spatial distribution of pixel values. These include co-occurrence and run-length matrices, local binary pattern and blob analysis[Quant text ref].

Measurement of motor unit activity using EMG

The Delsys Trigno surface EMG system will be used in this experiment. The system offers the benefit of having a 4-pin mini-grid that can extract individual motor unit data, without causing participants discomfort. The analysis will also be complemented by the use of intramuscular EMG, since it offers high location specificity when measuring EMG activity, while only a local region is analyzed. The intramuscular EMG data will be analyzed by a Cadwell Sierra Wave device.

The anatomical location for electrode placement, along the C7-acromion line, will be identified for each participant. Baseline EMG measurements, as well as the ultrasonic images will be taken from the upper trapezius muscle to obtain the baseline motor unit recruitment curve. The trapezius muscle was chosen for study since it is a common site for MTrPs, given the high load cervical muscles carry as well as the general increase sedentariness that perpetuates poor posture and cervical muscle strain, leading to trigger point presentation. Furthermore, the

trapezius muscle has been used frequently in previously published work, which analyze motor unit parameters, power spectrum and amplitude measurements.[31,32,33]

sEMG Analysis

After the identification for electrode placement and the captured baseline ultrasonic images, the area will be cleaned with alcohol and water. The Delsys Galelio sensor will be placed directly on the identified area. The EMG sensor (bandwidth of 20-450Hz) consists of 4 metal contacts for detecting the signal at the skin surface. Both the right and left sides of the trapezius will be measured.

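### Follow-up ultrasound comes after the post-intervention contractions and baseline ultrasound before any contraction, so the planned within-group texture test mixes contraction effects with sensitisation

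*Combined protocol and SAP*

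**What the plan says.** The order of the session comes mainly from the Experimental Protocol section.

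- Baseline imaging comes first: "The ultrasound probe will be placed on 3 muscles: the trapezius, the supraspinatus, and the infraspinatus. Two ultrasonic pictures will be taken of each".
- The skin is then cleaned and the EMG equipment applied: "The Delsys Galelio surface sensor, and the intramuscular needle electrode will be placed directly on the trapezius' identified area". The sEMG Analysis section confirms that images precede this step: "After the identification for electrode placement and the captured baseline ultrasonic images, the area will be cleaned with alcohol and water".
- Participants ramp up, hold and ramp down: "They will hold this contraction at 30% of their maximal voluntary contraction". On repetition: "This will be performed four times for each type of study intervention and before as well as after each intervention".
- The needle is removed and the participant bandaged. Then: "Following this, ultrasound pictures will be taken again from the same muscles mentioned previously".

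The Ultrasound analysis section is less specific: "The ultrasound probe will be placed onto the trapezius before and after the sensitization is induced and an ultrasonic image will be captured". No section describes an image between the sensitisation check and the second contraction block.

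Two safeguards are in the text. The Experimental Protocol asks for imaging away from muscle mechanically affected by the needle or the injection, without giving a distance or a marking rule. The section on inducing central sensitization provides cream-base and saline controls, and no different session is described for them.

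For analysis, the statistical analysis plan reduces the texture features by principal components and applies a repeated measures MANOVA for each intervention group. It states within-group and between-group testing for EMG, but no between-group contrast for texture.

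**The concern.** Texture change is the first primary outcome and answers research question a, whether sensitisation alters muscle structure. The two images that define it are separated by the intervention and also by two blocks of loaded contractions. A within-group test has no means of attributing a shift to one rather than the other.

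The ambiguity touches the trial's own interpretation. The Discussion sets out rival accounts in which muscle exertion or sustained low-threshold activation starts the process, and says that texture changes in the treated and regional muscles would support the neurogenic account. A shift caused by the task could be read as support for that account.

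**Working it through.** **1. What lies between the two images**

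| Step | Before baseline image | Before follow-up image |
|---|---|---|
| Needle electrode (trapezius only) | no | yes, placed and removed |
| Pre-intervention contractions | 0 | 4 |
| Intervention and wait (about 20 minutes, about 40 if repeated) | no | yes |
| Post-intervention contractions | 0 | 4 |

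The total of 4 + 4 = 8 assumes one intervention and that the four repetitions apply to each block. The argument needs only that the count is zero at baseline and above zero at follow-up.

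**2. What a within-group test does with a pure contraction shift**

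The plan gives no figure here to reproduce. The inputs are:

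- Group size: the sample size section gives 84 participants and 7 groups, so 84/7 = 12; the Study Design section speaks of six groups, so 84/6 = 14.
- Correlation between repeated measures: 0.5, from the sample size section. With equal variances, SD of change = SD × √(2(1 − 0.5)) = SD.
- Shift δ from contraction alone, in SD units: not in the documents. Assumed values are 0.2, 0.3, 0.5 and 0.8.

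For a paired t-test at two-sided 0.05, the noncentrality is λ = δ√n on n − 1 degrees of freedom. The rejection probability is P(|T| > critical value), where T is noncentral t. Critical values are 2.201 (n = 12) and 2.160 (n = 14).

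| δ | λ, n = 12 | Rejects | λ, n = 14 | Rejects |
|---|---|---|---|---|
| 0.2 | 0.693 | 9.7% | 0.748 | 10.7% |
| 0.3 | 1.039 | 15.8% | 1.122 | 18.0% |
| 0.5 | 1.732 | 35.3% | 1.871 | 41.0% |
| 0.8 | 2.771 | 71.4% | 2.993 | 79.0% |

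With δ = 0 the figure is 5%. These are for one texture component, not for the MANOVA.

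**3. What a between-arm contrast does with the same shift**

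If the shift is equal in capsaicin and control, it drops out of the difference in mean change and a two-sample test rejects at 5%. Only a difference Δ in the contraction effect between arms remains, with λ = Δ√(n/2) on 2n − 2 degrees of freedom:

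- Δ = 0.2: λ = 0.2 × √6 = 0.490 (n = 12) or 0.2 × √7 = 0.529 (n = 14); rejection 7.6% or 8.0%.
- Δ = 0.5: λ = 1.225 or 1.323; rejection 21.6% or 24.7%.

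The values of Δ are also assumptions.

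**4. Which block can produce a difference between arms**

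The first block is performed before the intervention, so randomisation balances its execution. Only the second block can be altered by capsaicin. Questions b and d hypothesise altered amplitude and recruitment, and the Discussion cites reorganised muscle activity after painful injection, so such a difference is plausible on the protocol's own terms.

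**The case against.** The strongest reply is that the trial has randomised controls who go through the same session. Shared contraction and EMG-needle effects therefore cancel on average once arms are compared, and the ramps are standardised: isometric, with exerted and target force displayed. This stands, and it limits the point. A reader might infer that the imaging order by itself makes sensitisation indistinguishable from exercise. The documents do not support that: the problem arises because the stated texture test is within group, plus whatever part of the second block capsaicin changes. Force feedback narrows that part but does not exclude it, since a given force can be reached with different muscle activity.

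A reader might also infer that needling contaminates all the images. The EMG needle enters only the trapezius, and the protocol already directs imaging away from needled or injected muscle. A residual effect there is possible because the instruction is not operationalised, but it is minor. Nor do the documents say how far the task loads the supraspinatus and infraspinatus; they say that the trapezius is contracted.

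One qualification concerns the controls themselves. The section on determining central sensitization withdraws participants who are not sensitised after a second application. Read literally, this could remove controls before follow-up imaging, and with them the cancellation.

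**Conclusion.** The point holds in this form: as the session and the analysis are written, within-group texture change cannot separate contraction from sensitisation. In a single-component paired test, the chance of declaring a change with no sensitisation effect is about 10% at an assumed shift of 0.2 SD and 71% to 79% at 0.8 SD. A reader might take the upper figure as the trial's false-positive rate. It is not: the documents give no exercise-related texture shift, it could be near zero, and the planned test is multivariate.

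With a between-arm contrast and controls retained, the remaining risk is much smaller: about 8% if capsaicin changes the contraction effect by 0.2 SD, and 22% to 25% if by 0.5 SD. Exact cancellation of the shared part also assumes similar waiting times in the arms, which the repeat-application rule could disturb if it is followed for controls.

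The order of steps is taken from the text. The timeline figure is not shown; if it differs, the two must be reconciled. For an exploratory trial this is a change that should be made, not one that invalidates the design.

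**What to change.** Make two changes.

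1. **Session order.** Keep the baseline images where they are. Take the follow-up images after the sensitisation check and before the post-intervention contractions. Mark the probe sites on the skin at baseline, clear of the planned sensor and needle positions, and use the same sites both times. This removes from the imaging interval the only contractions that capsaicin can alter. Record the time from application to image.
2. **Analysis.** State the primary texture test as a between-arm contrast of change: topical capsaicin versus cream base, and injected capsaicin versus saline. Separate before-after tests per group become descriptive. Reconcile the withdrawal rule with this contrast, which needs follow-up images from the controls.

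The first block stays inside the interval, but it precedes the intervention and is common to all arms, so the contrast deals with it. Moving the baseline images to just after that block is a tempting alternative that should be avoided: recovery from the contractions during the 20 to 40 minute wait would then enter the change score, and the baseline scan too would have to work around the sensor and needle.

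The cost is a wording change to the session and the analysis plan, with no additional images or participants. Post-intervention EMG starts a few minutes later, and at follow-up the trapezius probe must be placed clear of the sensor and needle.

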- e. Is there a location dependent EMG response to capsaicin induced sensitization? In other words, do the texture features or EMG responses from muscles that lie anatomically distant from the location of the site of intramuscular capsaicin injection have changes from their baseline calculations? This would test the hypothesis that type III and IV afferents have an influence on the anterior horn cells that lie distant to the ones that are supplying muscle fibers in the vicinity of the stimulated sensory afferents.
- f. Is there a dose dependent EMG response of motor units to capsaicin induced sensitization? Here, the hypothesis of causality will be assessed in a preliminary manner. If there is a relationship then further experiments that more thoroughly assess causality will be needed.

Methods & Design

Study Design:

The study conforms to the Consolidated Standards of Reporting Trials recommendations.

Ethical approval is approved by the University Health Network (UHN) Research Ethics Board.

This study is registered under the National Institutes of Health ClinicalTrials.gov.

This proposed study is a single centered, factorial, randomized placebo-controlled trial with two independent variables, depth of capsaicin application and dose of capsaicin, for a total of nine treatment arms. The first between groups variable will be topical capsaicin application

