and injectable capsaicin injection. Within each partition there will be three treatments: control, 50 micrograms, 100 micrograms. One-hundred micrograms reported to be an effective high dose of capsaicin.[13] The control group will receive a topical skin lotion which is inert and has no sensitization effect. An equal number of participants will be allocated to each of the six treatment groups using an electronic randomization generator. Block randomization will be used to ensure equal allotment into each group. An alternate member of the research team will conduct the randomization schedule a priori. Participant allocation will be concealed by placing their assignment in an envelope and delivered to participants by the same member of the research team uninvolved in the measurement or randomization protocols. Participants and investigators will be blinded to the delivered dose; however, the type of capsaicin delivery cannot be blinded from either participants or investigators. The member of the research team conducting the randomization schedule and concealing allocation will have knowledge of and keep track of the doses contained in the containers and vials of the topical and injectable capsaicin, respectively. They will deliver the appropriate dose to the team member implementing the experimental protocol to ensure there is blinding with respect to dose. This individual will not be involved in participant recruitment.

Participants

Recruitment

Participants will be recruited from UHN and the University of Toronto clinics, employees, volunteers, visitors, students, and external participants. UHN is a tertiary healthcare centre with eight hospitals located in Toronto, Canada and the University of Toronto is an academic institution with a main campus located in close proximity to the main UHN hospitals

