The Delsys Trigno system, which includes sensors, the Trigno base station, and the EMGworks software will be used to decompose the acquired EMG signals into individual motor units. The following parameters will be analyzed: the firing times and frequency of individual motor units, motor unit action potential amplitude and shapes[36-38], the root mean square value (RMS) of each channel and of the entire signal[16], the coefficient of variation for force steadiness[39], and the centroid of the EMG signal in the cranial-caudal and the medial-lateral directions[16]. This will be repeated for each contraction.

Intramuscular EMG analysis

A 27g monopolar electromyography needle will be placed into the midbelly of the upper fibers of the trapezius muscle using ultrasound guidance. The intramuscular EMG signals will be measured using Cadwell Sierra Wave. Since this system does not offer motor unit decomposition, we will use the intramuscular EMG analysis to provide us with more details of the gross EMG measurements such as the overall RMS value, the coefficient of variation for force steadiness, and the centroid measurements.

Determination of Central Sensitization:

Before measuring outcomes, approximately 20 minutes after capsaicin application we will analyze the area of secondary hyperalgesia for each study subject, then determine whether central sensitization has in fact been induced. The presence of central sensitization is confirmed by expansion of the receptive field and area of secondary hyperalgesia beyond the 25 cm² initial application area. If it has, the study participant will undergo the rest of the experimental methodology. If it has not, the capsaicin will be applied once more and the region of secondary hyperalgesia will be remeasured in 20 minutes later. The above described process for confirming the presence of central sensitization will take place again. If the study participant has not had sensitization at this stage they will be withdrawn from the study.

Primary Outcomes

The primary outcome measures:

1. Textural regional changes
2. Recruitment and Amplitude regional changes

These will be recorded for each arm of the study, please see figure 1.

Secondary outcomes:

1. A record of adverse events

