texture features will be computed in MATLAB and principal component analysis will be computed to reduce the variables. A repeated measures MANOVA will be applied for each intervention group. To test the change in EMG within and between groups a repeated measurement ANOVA will be applied considering each intervention group as a factor. The dependent variable would be considered as pain intensity, duration, and area of pain in separate analysis. Data distributions would be first checked with the Shapiro-Wilk to conform the normal distribution of the data. Additionally, we will test for the homogeneity of variance using Mauchly's test as well as correcting the degrees of freedom if necessary [40]. If the assumption of normality not met, for all skewed data an appropriate transformation will be used. We will construct univariate and multivariable linear regression models of differences in EMG amplitude (differences between after and before) as a function of intervention groups when adjusted for important covariates. Due to small sample size in each group, there is not possible to adjust for several covariates. Therefore, in a univariate model we will find the most important ones. For initial selection of relevant variables, all variables with a p-value ≤ 0.2 in the univariate analysis will be selected and retained in the multivariable analysis.

All Statistical analyses will be conducted with SAS for Windows (version 9.3; SAS Institute, Inc, Cary, NC). Using a two-sided test a P-value ≤ 0.05 will be considered as statistically significant.

Discussion

This will be the first study that assesses the effect of capsaicin induced central sensitization on ultrasound texture features and muscle motor unit activity. Findings from this

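### Re-applying capsaicin to participants who miss the sensitisation criterion means the randomised arms no longer compare 50 with 100 micrograms, and the analysis plan does not account for it

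*Combined protocol and SAP*

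**What the plan says.** Study Design fixes the dose levels within each route: "Within each partition there will be three treatments: control, 50 micrograms, 100 micrograms". Research question f, at the end of the Background, rests on that contrast: "Is there a dose dependent EMG response of motor units to capsaicin induced sensitization". The protocol treats f as a preliminary look at causality.

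Determination of Central Sensitization then adds a rule that acts after randomisation. "Before measuring outcomes, approximately 20 minutes after capsaicin application we will analyze the area of secondary hyperalgesia for each study subject". The criterion is an "area of secondary hyperalgesia beyond the 25 cm² initial application area", and it is the same in every arm. For a participant who does not meet it, the rule is: "If it has not, the capsaicin will be applied once more and the region of secondary hyperalgesia will be remeasured in 20 minutes later". After a second failure: "If the study participant has not had sensitization at this stage they will be withdrawn from the study". The size of the repeat dose is not stated.

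For EMG, the statistical analysis plan says that "a repeated measurement ANOVA will be applied considering each intervention group as a factor". It also plans regressions of the after-minus-before amplitude on intervention group. Neither analysis refers to a second application, cumulative dose or time since application.

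The section on inducing central sensitisation gives the control treatments as the cream base without capsaicin, or saline.

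**The concern.** The dose a participant receives becomes a consequence of how that participant responded. Outcomes are read only after participants in both dose arms have been pushed towards one threshold. The protocol's own premise is that capsaicin "elicits a dose dependent pain responses, allowing for more easily quantifiable measurements". If that extends to the area of secondary hyperalgesia, more of the 50 microgram arm will fail the first check and be re-applied. The low arm is then moved up more often than the high arm, before the comparison meant to detect a dose effect is made.

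At stake is the reading of question f. A small difference between arms could mean that dose does not matter, or that the rule brought the arms together. The planned analysis cannot separate the two.

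There is also a conflict of wording. The re-application rule covers any participant who fails and refers to capsaicin, whereas controls are elsewhere given only vehicle or saline.

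**Working it through.** The plan gives no re-application rate or dose-contrast figure to reproduce. Its sample size (70, raised to 84) makes no allowance for re-application and does not bear on this point.

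**Inputs from the documents.** Doses of 50 and 100 micrograms; one repeat at most; one criterion for all arms; checks about 20 minutes after each application.

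**Assumptions.** The repeat equals the assigned dose. The shares re-applied, r50 and r100, are not in the documents and are varied.

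**Step 1, total dose.** A re-applied 50 microgram participant totals 50 + 50 = 100, the same as a once-treated participant in the high arm. A re-applied 100 microgram participant totals 100 + 100 = 200. The overlap is therefore partial.

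**Step 2, mean gap between arms.**
- In micrograms: 100(1 + r100) − 50(1 + r50) = 50 + 100·r100 − 50·r50. This falls below 50 only if r50 > 2·r100.
- In log2 dose: 1 + r100 − r50. This falls below 1 whenever r50 > r100.
- Examples (r50/r100): 0.6/0.2 gives means of 80 and 120, gap 40. 0.2/0.1 gives 60 and 110, gap 50. 0.3/0.3 gives 65 and 130, gap 65.

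**Step 3, effect on the outcome contrast, nobody withdrawn.** Let the outcome be proportional to a sensitisation index with total variance 1 (0.75 between persons, 0.25 between occasions) and threshold 0. The first-check pass rate in an arm fixes its mean m = Φ⁻¹(pass rate). The true contrast is δ = m100 − m50. If the repeat adds δ in both arms (log-dose), an arm's final mean is m + δ·r + 0.25·φ(m). The last term arises because re-applied participants are measured on a fresh occasion. The fraction of the contrast retained is

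1 + r100 − r50 + 0.25·[φ(m100) − φ(m50)]/δ.

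If the repeat adds 2δ in the 100 microgram arm (linear in micrograms), r100 is replaced by 2·r100.

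| Pass rates 50/100 | r50/r100 | δ | Last term | Log dose | Linear |
|---|---|---|---|---|---|
| 30%/60% | 0.7/0.4 | 0.778 | +0.012 | 0.71 | 1.11 |
| 50%/80% | 0.5/0.2 | 0.842 | −0.035 | 0.66 | 0.86 |
| 70%/90% | 0.3/0.1 | 0.757 | −0.057 | 0.74 | 0.84 |

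For the middle row: 1 + 0.2 − 0.5 − 0.035 = 0.665 for log dose, and 1 + 0.4 − 0.5 − 0.035 = 0.865 for linear.

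**Step 4, timing.** The check that releases a participant to outcome measurement falls about 20 minutes after the last application for everyone. Counted from the first application it is about 20 minutes for early responders and 20 + 20 = 40 for those re-applied.

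**Step 5, margin.** With 84/7 = 12 per arm (an assumption, since Study Design counts six groups), a two-sided 5% comparison of 50 with 100 micrograms has power 0.231 at a standardised difference of 0.5. If that shrinks to 0.35 (70% of it), power is 0.135.

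**The case against.** The strongest reply is that the direction of bias is not established, and this stands. The repeat dose is unstated. If it equals the assigned dose, the high arm also moves up, and on the microgram scale the contrast can widen. A reader might infer that the rule necessarily biases question f towards no effect; the documents do not support that.

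A reader might also quote larger losses. Under the same model, restricting to participants who stay in after the second check leaves only 29% to 61% of the contrast. That range includes the effect of withdrawing those who fail twice, which is a separate matter. It also depends on a log-dose repeat and on an outcome that follows the gating index itself, so it should not be attributed to re-application.

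Two further inferences go too far. Unequal timing is not a demonstrated bias: the interval from the last application is about the same for all, and the documents do not show how the longer interval from the first would act. Nor do the documents show that controls would be given capsaicin. The wording is ambiguous, and the description of the control treatments points the other way.

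Finally, f is one of six questions in an exploratory trial, is to be addressed only in a preliminary way, and has little power even undiluted. That limits the weight of the point but does not remove it: the rule is explicit, and an analysis by intervention group would still be reported as a dose comparison that was not delivered.

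**Conclusion.** The concern holds as a matter of what the arm contrast estimates. Following the plan as written, received dose depends on post-randomisation response, and the contrast for question f compares regimens with conditional re-application, not 50 with 100 micrograms. This follows from the text and needs no assumed rates.

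The size and direction do rest on assumptions: pass rates from 30%/60% to 70%/90%, a repeat equal to the assigned dose, and an outcome proportional to the sensitisation index. On these, re-application alone retains about 66% to 74% of the true contrast if response is linear in log dose and about 84% to 111% if linear in micrograms. Attenuation is the more plausible outcome under the protocol's dose-dependence premise, but inflation cannot be excluded. The point is worth correcting before analysis; it does not invalidate the trial's other questions.

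**What to change.** 1. Reconcile Study Design, the section on inducing central sensitisation and the section on determining it. They should agree on what the randomised dose means once re-application occurs, what is given at the repeat, and what a control participant receives. The clinical content is for the investigators to settle.
2. Record for every participant the number of applications, the cumulative micrograms, and the times from first and last application to outcome measurement. Report these by arm.
3. In the analysis plan, analyse question f by randomised arm. Describe the result as a comparison of assigned regimens including re-application, not as a fixed 50 versus 100 microgram effect.
4. Add a descriptive summary by dose received, labelled as non-randomised.

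The cost is a little extra recording, some added wording and a more cautious dose-response conclusion. No extra participants or procedures are needed.

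Taking a full outcome set at the first check, before any re-application, would isolate the single-application contrast. It would also add needle EMG and contractions for those re-applied, delay the repeat, and bring non-sensitised participants into a question about the response to sensitisation. That is a trade-off for the investigators and is not needed for this correction.
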